##### 14.1.2.1. Derivations

Refer to Section 14.1.1.1: Derivations for relevant derivations, the following information is specific to the ChAd3 neutralisation data:

- Log-transformed titre values and serological status:
  - o The relevant cut-off value is the reciprocal titre of 12.
- Response:
  - o Yes:  
For seronegative pre-vaccination: Post-vaccination titre value of at least the assay cut-off\* value.

---

Document: CHAD3-004-EBO-Z\_Interim\_Final\_SAP\_v2\_0  
Author: PPD Version Number: 2.0 Version Date: 14JUN2017

Template No: CS\_TP\_BS016 – Revision 3  
Effective Date: 01May2012

Reference: CS\_WI\_BS005

For seropositive pre-vaccination: Post-vaccination titre value of at least x-fold\* increase over the pre-vaccination titre value. o No:

For seronegative pre-vaccination: Post-vaccination titre value of less than the assay cut-off\* value.

For seropositive pre-vaccination: Post-vaccination titre value of less than x-fold\* increase over the pre-vaccination titre value.

NOTE: Assay cut-off value is defined as 12.

NOTE: x-fold is defined as 3-fold.

- Above threshold:
  - o Yes:  
Post-vaccination value  $\geq$  defined threshold.
  - o No:  
Post-vaccination value  $<$  defined threshold.
  - o The threshold value is 200.

## 14.2. CELL-MEDIATED IMMUNITY (CMI) AGAINST EBOLA

### 14.2.1. CHAd3-EBOV-SPECIFIC CD4+ OR CD8+ T-CELL RESPONSE

The following listing is planned for presentation for the Total Vaccinated Cohort: Immunogenicity:

- ChAd3-EBOV-specific results.

The following table is planned for presentation for the According-to-protocol Cohort:

- ChAd3-EBOV-specific response.
  - o The number and percentage (%) of subjects in each response category (yes, no).
  - o Percentage (%) calculated relative to the number of subjects with results available in order to assign a status at each time point.
  - o 95% CIs for the response rates will be presented for each treatment group.
  - o This table will be presented by T-cell:
    - CD4+.
    - CD8+.
  - o The overall post-baseline response rate will also be included (response at any time point postbaseline).
- Frequency of ChAd3-EBOV-specific T-cells per subset.
  - o Summary statistics, refer to Section 6.6: Statistical Tests, based on the percentage results per subset.

---

Document: CHAD3-004-EBO-Z\_Interim\_Final\_SAP\_v2\_0  
Author: PPD Version Number: 2.0 Version Date: 14JUN2017

Template No: CS\_TP\_BS016 – Revision 3  
Effective Date: 01May2012

Reference: CS\_WI\_BS005

- Coexpression profile of Ebola Zaire antigen specific CD4+ T-cells using each possible combination of cytokines (IFN, IL2, TNF) and levels expressed in percentages:
  - o Summary statistics, refer to Section 6.6: Statistical Tests, based on the percentage results per subset.
  - o Immune markers with at least one positive cytokine will be presented:
    - IFN+IL2+TNF+
    - IFN+IL2+TNF-
    - IFN+IL2-TNF+
    - IFN+IL2-TNF-      IFN-
    - IL2+TNF+
    - IFN-IL2+TNF-
    - IFN-IL2-TNF+ o This table will be repeated for the CD8+ T-cells. o
    - This table will be repeated for the pooled data following the EBO-Z vaccination.
- Percentage of Ebola Zaire antigen-specific CD4+ T-cells using expressing at least 1 cytokine, 1, 2 and 3 cytokines:
  - o Summary statistics, refer to Section 6.6: Statistical Tests, based on the percentage results per subset.
  - o Immune markers with at least one positive cytokine will be presented:
    - CD4+ T cells expressing at least 1 cytokine
    - CD4+ T cells expressing 1 cytokine
    - CD4+ T cells expressing 2 cytokines
    - CD4+ T cells expressing 3 cytokines o This table will be repeated for the CD8+ T-cells. o
    - This table will be repeated for the pooled data following the EBO-Z vaccination.

All CMI tables will be presented by Baseline anti-GP EBOV serological status, including the following categories:

- Seronegative.
- Seropositive.
- Total.

The following figures are planned for presentation for the According-to-protocol Cohort (CMI sub-cohort):

- Coexpression profile of Ebola Zaire antigen specific CD4+ T cells using each possible combination of cytokines (IFN, IL2, TNF) and levels expressed in percentages:
  - o The % of cell expressing 1, 2 or 3 markers would be presented o Median and Q1 as well as Q3 will be presented.
  - o This figure will be repeated for the CD8+ T-cells.
- Percentage of Ebola Zaire antigen specific CD4+ T-cells using expressing at least 1 cytokine, 1, 2, and 3 cytokines:
  - o Pie charts presenting the relative % of cells expressing 1, 2 or 3 cytokine.

Document: CHAD3-004-EBO-Z\_Interim\_Final\_SAP\_v2\_0

Author: PPD Version Number: 2.0 Version Date: 14JUN2017

Template No: CS\_TP\_BS016 – Revision 3

Reference: CS\_WI\_BS005

Effective Date: 01May2012

- o Size of the pie chart will be scaled to the geometric mean. o Day 0 and Day 30
- o results presented next to one another on the same figure. o Separate pie charts
- o presented for the treatment groups on the same page. o This figure will be repeated for the CD8+ T-cells.

The following immunology variables, as presented in the planned TLF shells, will be collected on the Blood Sampling form in eSource:

- Were CMI blood samples collected:
  - o Yes.
  - o No.
- Date and time of sample collection.

The following immunology variables, as presented in the planned TLF shells, will be imported from the laboratory report:

- Subset:
  - o CD4+/IFN. o CD4+/IL2. o CD4+/TNF. o
  - o CD8+/IFN. o CD8+/IL2.
  - o CD8+/TNF.
- Antigen:
  - o GP(Z1). o GP(Z2).
  - o NEG.
- Results, per T-cell and antigen:
  - o Total number of cells (NSUB result).
- Results, per subset and antigen:
  - o Percentage result (PCTPOS result).
  - o Adjusted result (%) (AD\_PCTPOS result):  
Per subset and antigen, percentage result minus the NEG antigen percentage result.

#### 14.2.1.1. Derivations

Based on the aforementioned immunogenicity variables, the following variables, as presented in the planned TLF shells, will be derived:

- Baseline serological status:
  - o Based on the pre-vaccination anti-GP EBOV serological status:  
Seronegative.  
Seropositive.
- T-cell frequency (%):

---

Document: CHAD3-004-EBO-Z\_Interim\_Final\_SAP\_v2\_0  
Author: PPD Version Number: 2.0 Version Date: 14JUN2017

Template No: CS\_TP\_BS016 – Revision 3  
Effective Date: 01May2012

Reference: CS\_WI\_BS005

- o Per subset, sum of the GP(Z1) and GP(Z2) adjusted result (%) for analysis.
- o Negative T-cell frequencies will be set to 0.0001% for analysis purposes.
- Number of positive cells:
  - o Per subset and antigen the number of positive cells is derived by multiplying the total number of cells (NSUB) with the percentage of cells (PCTPOS), if this result is not an integer due to rounding issues, the result will be rounded to the nearest integer:  

$$\text{Positive cells} = \text{ROUND}(\text{NSUB} \times (\text{PCTPOS} \times 0.01), 1.0).$$
- Number of negative cells:
  - o Per subset and antigen, once the number of positive cells is calculated, the negative cells is derived as the difference between the total number of cells (NSUB) and the positive number of cells.
- Response:
  - o No:
 

Per subset and antigen (excluding the NEG antigen), a Fisher's exact test is performed for the 2x2 table consisting of positive and negative cells compared to that of the negative control (NEG antigen) and the one-sided p-value is > 0.01.

OR

The one-sided p-value is <= 0.01 and adjusted result (%) is smaller than or equal to the values provided in Table 4: Adjusted Result (%) Response Criteria below.
  - o Yes:
 

Per subset and antigen (excluding the NEG antigen), a Fisher's exact test is performed for the 2x2 table consisting of positive and negative cells compared to that of the negative control (NEG antigen) and the one-sided p-value is <= 0.01.

AND

The adjusted result (%) is larger than the value provided in Table 4: Adjusted Result (%) Response Criteria below.

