#### 14.1.1.1. Derivations

Based on the aforementioned immunogenicity variables, the following variables, as presented in the planned TLF shells, will be derived:

- Log-transformed concentration values:
  - o Log10 of the concentration values will be derived.
  - o Results below the cut-off of the assay will be assigned as half of the cut-off\* value before taking the log for analysis purposes.
- Serological status:
  - o Seronegative:  
Concentration value is below the cut-off\* value.
  - o Seropositive:  
Concentration value is greater or equal to the cut-off\* value.
  - o Seroconversion:  
Seropositive result post-vaccination for any subjects defined as seronegative pre-vaccination.
- Response:
  - o Yes:  
For seronegative pre-vaccination: Post-vaccination concentration value of at least the assay cutoff value.  
For seropositive pre-vaccination: Post-vaccination concentration value of at least x-fold increase over the pre-vaccination concentration value.
  - o No:  
For seronegative pre-vaccination: Post-vaccination concentration value of less than the assay cutoff value.  
For seropositive pre-vaccination: Post-vaccination concentration value of less than x-fold increase over the pre-vaccination concentration value.

The x-fold increase will be calculated as:

$$= \frac{\text{Post-vaccination concentration value}}{\text{Pre-vaccination concentration value}}$$

Document: CHAD3-004-EBO-Z\_Interim\_Final\_SAP\_v2\_0

Author: PPD Version Number: 2.0 Version Date: 14JUN2017

Template No: CS\_TP\_BS016 – Revision 3

Reference: CS\_WI\_BS005

Effective Date: 01May2012

NOTE: Assay cut-off value is defined as 36.11 EU/mL.

NOTE: x-fold is defined as 3-fold.

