**Table 4: Adjusted Result (%) Response Criteria**

T-cell	Cytokine	Criteria
CD4+	IFN	0.05
	IL-2	
	TNF	
CD8	IFN	0.08
	IL-2	0.05
	TNF	0.08

Document: CHAD3-004-EBO-Z\_Interim\_Final\_SAP\_v2\_0  
 Author: PPD Version Number: 2.0 Version Date: 14JUN2017

Template No: CS\_TP\_BS016 – Revision 3  
 Effective Date: 01May2012

Reference: CS\_WI\_BS005

If at least one of the subset and antigen combinations has a response derived as Yes, the subject is considered as a responder for that visit. If the subject is response at least one post-baseline visit, the subject will be regarded as an overall responder.

For the table pooled following the EBO-Z vaccination the overall response rate will only consider post-vaccination responses with 6 month of the EBO-Z vaccination:

- EBO-Z/MENACWY-TT treatment group:
  - o Day 30. o  
Month 6.
- MENACWY-TT/EBO-Z treatment group:
  - o Month 6 +  
30 days. o  
Month 12.

If either of the aforementioned post-vaccination responses has been derived as Yes, the subject will be considered as an overall responder for the pooled table.

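### The overall T-cell responder rows ignore each child's sample before ChAd3-EBO-Z, so children who were already positive, and some controls positive only before the vaccine, count as responders

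*SAP*

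**What the plan says.** SAP v2 section 14.2.1.1 sets Response to Yes, for each cytokine subset and peptide pool, when two conditions hold. The first is a Fisher test, one-sided at 0.01, on a "2x2 table consisting of positive and negative cells compared to that of the negative control (NEG antigen"). The second is a fixed size limit: "The adjusted result (%) is larger than the value provided in Table 4: Adjusted Result (%) Response Criteria below". Section 14.2.1 says what is subtracted: "Per subset and antigen, percentage result minus the NEG antigen percentage result". The Table 4 limit is 0.05 for the three CD4+ cytokines and for CD8 IL-2, and 0.08 for CD8 IFN and CD8 TNF.

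The text after Table 4 builds this up. The visit-level step reads: "If at least one of the subset and antigen combinations has a response derived as Yes, the subject is considered as a responder". A child positive at one or more post-baseline visits is an overall responder. For the pooled table the qualifying visits are Day 30 and Month 6 in EBO-Z/MENACWY-TT, and Month 6 + 30 days and Month 12 in MENACWY-TT/EBO-Z: "If either of the aforementioned post-vaccination responses has been derived as Yes, the subject will be considered as an overall responder".

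The anti-GP antibody rule in section 14.1.1.1 does use the pre-vaccination sample: "For seropositive pre-vaccination: Post-vaccination concentration value of at least x-fold increase over the pre-vaccination concentration value", with x set to 3. The ChAd3 neutralisation rule in section 14.1.2.1 does the same.

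Cell-mediated immunity (CMI) blood is planned at Day 0, Day 30, Month 6, Month 6 + 30 days and Month 12 in about 90 children per group. CMI tables are split by baseline anti-GP serostatus. Protocol section 11.3 lists the responder rate as a tertiary endpoint without defining it.

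**The concern.** The tertiary objective is the EBOV-specific cellular response to one dose of ChAd3-EBO-Z, so a reader will take an overall responder to be a child in whom the vaccine induced a response. The rule cannot show that. Every input to it comes from one visit, and the child's state before ChAd3-EBO-Z is not among them.

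A child can be counted without any vaccine effect in two ways:

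- **Persistent positivity.** A child positive before ChAd3-EBO-Z and unchanged afterwards is Yes again at a qualifying visit.
- **Wrong visits.** SAP section 6.2 sets baseline before the first vaccination. For MENACWY-TT/EBO-Z, the by-group row over any post-baseline time point therefore includes Day 30 and Month 6. Both precede that group's ChAd3-EBO-Z dose: SAP Table 2 makes Month 6 its time zero, and the pooled rule leaves it out. At the final analysis this row is neither a vaccine rate nor a control rate.

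The antibody sections require a 3-fold rise in children already positive. The SAP gives no reason for having no counterpart for T-cells.

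**Working it through.** The documents give no expected responder rate, background, cell count or baseline T-cell prevalence, so there is no stated figure to reproduce. Values marked as assumed are mine.

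**1. One unchanged child.** Assume CD4+/IFN at 0.10% on peptide and 0.02% on NEG, at both Day 0 and Day 30. The adjusted result is 0.10 - 0.02 = 0.08%, above 0.05.

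- 20,000 cells: 20 against 4 positive cells, one-sided p = 7.7e-4.
- 50,000 cells: 50 against 10 positive cells, p = 8.0e-8.

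The result is Yes at both visits, so the child is an overall responder with zero change. A child who falls from 0.20% to 0.10% (50,000 cells) is also Yes at Day 30, with the same p = 8.0e-8. For CD8 IFN or TNF the same 0.08% would be No, because it does not exceed 0.08.

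**2. How often an unchanged response is called Yes again.** I simulated three cytokines by two pools with a NEG count shared within each cytokine, a true response in one combination, and 20,000 runs per cell. Background is assumed to be 0.02%. The limits are those of Table 4.

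| True response above background | 20,000 cells | 50,000 cells | 150,000 cells |
|---|---|---|---|
| 0.06%, limit 0.05 | 58% | 73% | 88% |
| 0.08%, limit 0.05 | 82% | 97% | 100% |
| 0.10%, limit 0.05 | 94% | 100% | 100% |
| 0.06%, CD8 IFN/TNF limit 0.08 | 16% | 7% | 1% |
| 0.08%, CD8 IFN/TNF limit 0.08 | 45% | 47% | 48% |
| 0.10%, CD8 IFN/TNF limit 0.08 | 75% | 88% | 98% |
| No response, all limits 0.05 | 0.1% | 0.0% | 0.0% |

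Persistence is likely when the response is clearly above the limit that applies, and not otherwise. The last row covers counting noise only, which almost never passes both conditions.

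**3. Effect on the rate.** Let b be the proportion persistently positive before ChAd3-EBO-Z and v the true response rate among the others. The reported rate is b + (1 - b)v. The share of all children who newly respond is (1 - b)v, so the excess is b.

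With v = 0 and 180 children (b assumed):

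- b = 2%: 0.02 x 180 = 3.6, about 4 children.
- b = 5%: 9 children (exact 95% CI 2.3% to 9.3%).
- b = 10%: 18 children (exact 95% CI 6.0% to 15.3%).

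With b = 10% and v = 60%, the reported rate is 0.10 + 0.90 x 0.60 = 64.0%, against 54.0% of children newly responding. Against the 60% response rate among children negative beforehand, the excess is 4 points, that is b(1 - v).

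**The case against.** The strongest reply is that this is an assay-positivity rate, honestly described as such, and that the plan already shows what a reader needs. Responder status is tabulated at each time point, Day 0 included, with intervals per group. Nimenrix recipients at Day 30 and Month 6 are a concurrent control for the by-visit rates. The pooled tables have a time point at 0 days post-vaccination, T-cell frequencies are summarised, and individual results are listed. Previous investigational EBOV or Marburg vaccination, known EBOV or SUDV disease and recent exposure are exclusions (protocol section 4.4), so baseline T-cell positivity may be rare. The protocol never defines responder rate as vaccine-induced, and an antibody rule does not bind a different assay.

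Much of this stands. The by-visit rates can be interpreted, and they would reveal a baseline problem at group level. They do not repair the overall rows, because separate visit rates cannot show which overall responders were already positive. The pooled table has no control column (protocol section 11.9). Anti-GP serostatus is not T-cell status. The SAP's reference list names an ICS positivity criteria document that is not available here; nothing in the SAP says that it adds a comparison with baseline.

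It is also fair that counting only children who go from No to Yes would drop true boosts, and would let a marginal pre-dose result remove a child.

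**Conclusion.** The point holds for the overall and pooled responder rows, not for the by-visit table. Those rows mix vaccine-induced responses with persistent earlier positivity. The by-group row for MENACWY-TT/EBO-Z also counts positives from before ChAd3-EBO-Z. The excess is about b, which is unknown; if b is near zero, the persistent-positivity part is negligible. The re-firing probabilities rest on the assumed background and cell counts.

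Three stronger readings are tempting and not supported:

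- **That noise builds up over visits, so the overall row must exceed the pre-vaccination rate even for an inert vaccine.** Under the stated assumptions counting noise gives about 0.1% per visit or less. With stable positives the overall row is about equal to the pre-vaccination rate. Other sources of sporadic positives are possible, but the documents give no rate for them.
- **That any unchanged response is nearly certain to be counted again.** That is true only well above the limit. A CD8 IFN response of 0.06% is called Yes again in 1% to 16% of runs.
- **That many children are positive at baseline.** No figure in the documents supports a particular prevalence.

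The endpoint is tertiary and all analyses are descriptive (SAP section 7.4). No confirmatory conclusion is affected, and priority is low.

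**What to change.** In SAP v2 section 14.2.1.1, separately for CD4+ and CD8+:

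1. Derive T-cell status (Yes/No) at the last sample before ChAd3-EBO-Z: Day 0 for EBO-Z/MENACWY-TT and Month 6 for MENACWY-TT/EBO-Z. State that the Month 6 sample is drawn before the dose.
2. Present the overall and pooled responder rows by that status, and read the vaccine-induced rate from the children who were No.
3. For children already Yes, show the change in T-cell frequency, so that boosts stay visible.
4. Limit the by-group overall row to visits after ChAd3-EBO-Z. Report Day 30 and Month 6 of MENACWY-TT/EBO-Z separately as the control rate. This also shows how often a child near the limit moves from No to Yes without ChAd3-EBO-Z.
5. Keep the by-visit positivity table unchanged.

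The cost is one extra derivation and smaller strata, with wider intervals. No new blood, visits or assays are needed. Relabelling the row as positive at any post-dose visit would be cheaper, but it would leave the question about the vaccine unanswered.

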**Table 4: Adjusted Result (%) Response Criteria**

T-cell	Cytokine	Criteria
CD4+	IFN	0.05
	IL-2	
	TNF	
CD8	IFN	0.08
	IL-2	0.05
	TNF	0.08

Document: CHAD3-004-EBO-Z\_Interim\_Final\_SAP\_v2\_0  
 Author: PPD Version Number: 2.0 Version Date: 14JUN2017

Template No: CS\_TP\_BS016 – Revision 3  
 Effective Date: 01May2012

Reference: CS\_WI\_BS005

If at least one of the subset and antigen combinations has a response derived as Yes, the subject is considered as a responder for that visit. If the subject is response at least one post-baseline visit, the subject will be regarded as an overall responder.

For the table pooled following the EBO-Z vaccination the overall response rate will only consider post-vaccination responses with 6 month of the EBO-Z vaccination:

- EBO-Z/MENACWY-TT treatment group:
  - o Day 30. o  
Month 6.
- MENACWY-TT/EBO-Z treatment group:
  - o Month 6 +  
30 days. o  
Month 12.

If either of the aforementioned post-vaccination responses has been derived as Yes, the subject will be considered as an overall responder for the pooled table.

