**Synopsis Table 2 Treatments foreseen in the study**

Treatment name	Vaccine/Product name	Study Groups	
		EBO-Z/ MENACWY-TT	MENACWY-TT/ EBO-Z
ChAd3-EBO-Z	ChAd3-EBO-Z	x (Day 0)	x (Month 6)
Nimenrix	MenACWY-TT ----- NaCl	x (Month 6)	x (Day 0)

**ChAd3-EBO-Z** = investigational recombinant chimpanzee adenovirus type 3-vectored Ebola virus Zaire (EBOV) vaccine; **MenACWY-TT** = meningococcal serogroups A, C, W-135, Y tetanus toxoid conjugate vaccine; **NaCl** = sodium chloride

- **Control:** Active control (*Nimenrix*).
- **Vaccination schedule:** All subjects will receive 2 vaccinations, 1 at the Day 0 visit and 1 at the Month 6 visit. All subjects will receive 1 dose of the investigational ChAd3-EBO Z vaccine and 1 dose of *Nimenrix*:
  - Subjects in Group EBO-Z/ MENACWY-TT will receive the investigational ChAd3-EBO-Z vaccine at the Day 0 visit and *Nimenrix* at the Month 6 visit.
  - Subjects in Group MENACWY-TT/ EBO-Z will receive *Nimenrix* at the Day 0 visit and the investigational ChAd3-EBO-Z vaccine at the Month 6 visit.

- **Treatment allocation:** Subjects will be randomised (1:1) at Day 0. In order to ensure equal distribution of the population, enrolment will be stratified by age so that an equal number of children are enrolled in each age stratum (1 to 5 years, 6 to 12 years, and 13 to 17 years of age). In addition, the randomisation will use a minimisation procedure accounting for gender and centre.
- **Staggered vaccination:** Vaccination at Day 0 will be done in a staggered manner, starting with vaccination of the children in the oldest age stratum (13 to 17 years of age). In order to proceed to vaccination of the subjects in the younger age stratum (6 to 12 years of age), possibly with a lower vaccine dose, a favourable outcome of the IDMC review of safety data up to at least 7 days after vaccination from at least 50 subjects (25/ group) in the oldest age stratum needs to be obtained. The same will be done for moving from the 6 to 12 years of age stratum to vaccination of the youngest children (1 to 5 years of age).
- **Blinding:**
  - **Observer-blind** from study start until the interim analysis that will be conducted when safety, reactogenicity and immunogenicity (including at least anti-GP EBOV data at Day 30) data is available from all subjects up to 30 days after vaccination at Day 0.
  - **Single-blind** as of the interim analysis *at Day 30*.  
(Amended 06 May 2015.)
- **Sampling schedule:**

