## 5.5. SUB-COHORTS AND SUBSETS OF SUBJECTS

### 5.5.1. SUB-COHORT FOR CELL-MEDIATED IMMUNITY (CMI)

---

Document: CHAD3-004-EBO-Z\_Interim\_Final\_SAP\_v2\_0  
Author: PPD Version Number: 2.0 Version Date: 14JUN2017

Template No: CS\_TP\_BS016 – Revision 3  
Effective Date: 01May2012

Reference: CS\_WI\_BS005

The first approximately 30 subjects randomised per age stratum and group, (180 subjects in total, 90 per group) will be included in this sub-cohort. Subjects will be included from selected centres (refer to Section 7.2: Multicentre Studies) only. A blood sample for assessment of CMI should be taken from the subjects at the following visits:

- Day 0.
- Day 30.
- Month 6.
- Month 6 + 30 days.
- Month 12.

This sub-cohort will be programmatically assigned based on the relevant treatment allocation information recorded on the Visit Day 0 form in eSource. This sub-cohort will be labelled as the CMI Sub-cohort in the relevant presentations.

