### 6.2. BASELINE

Unless otherwise specified, Baseline is defined as the last non-missing assessment (scheduled or unscheduled) prior to the first vaccination. In the case where the last non-missing assessment and the reference start date coincide, that assessment will be considered pre-baseline (unless specified as post-vaccination). However, adverse events (AEs) starting on the reference start date will be considered post-baseline.

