### 6.3. DERIVED TIME POINTS

#### 6.3.1. CHAd3-EBO-Z POST-VACCINATION TIME POINTS

As a first step, safety and/or immunogenicity results will be presented by treatment administered at Day 0.

In a second step, all available data post-vaccination with the investigational vaccine (Day 0 for the EBOZ/MENACWY-TT and Month 6 for the MENACWY-TT/EBO-Z treatment groups, respectively) will be pooled. All available safety and immunogenicity data following the ChAd3-EBO-Z vaccination in both the treatment groups will be pooled at the time points as specified in Table 2: Derivation of ChAd3-EBO-Z Post-vaccination Time Points:

Table 2: Derivation of ChAd3-EBO-Z Post-vaccination Time Points

---

Document: CHAD3-004-EBO-Z\_Interim\_Final\_SAP\_v2\_0  
Author: PPD Version Number: 2.0 Version Date: 14JUN2017

Template No: CS\_TP\_BS016 – Revision 3  
Effective Date: 01May2012

Reference: CS\_WI\_BS005

ChAd3-EBO-Z Post-vaccination Time Point	Treatment Group	Visit
0 Days Post-vaccination with EBO-Z	EBO-Z/MENACWY-TT	Day 0
	MENACWY-TT/EBO-Z	Month 6
6 Days Post-vaccination with EBO-Z	EBO-Z/MENACWY-TT	Day 6
	MENACWY-TT/EBO-Z	Month 6 + 6 Days
30 Days Post-vaccination with EBO-Z	EBO-Z/MENACWY-TT	Day 30
	MENACWY-TT/EBO-Z	Month 6 + 30 Days
3 Months Post-vaccination with EBO-Z	EBO-Z/MENACWY-TT	Month 3
	MENACWY-TT/EBO-Z	Month 9
6 Months Post-vaccination with EBO-Z	EBO-Z/MENACWY-TT	Month 6
	MENACWY-TT/EBO-Z	Month 12

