#### 15.4.1. DERIVATIONS

Based on the aforementioned variables, the following variables will be derived:

- Relative day:
  - o Calculated relative to Day 0 vaccination (refer to Section 6.1: Reference Start Date and Relative Day).
- Change from Baseline for results in System of International (SI) units (refer to Section 6.7.1: Change from Baseline).
- Derived decrease categories (%):
  - o  $\text{Change from Baseline} / \text{value at Baseline} \times 100$
- Toxicity grade for selected laboratory tests (refer to APPENDIX 6: Laboratory Toxicity Grading for derivation details).
  - o Maximum grade overall will also be derived as the highest post-vaccination toxicity grade across all post-baseline visits and time points.
- Reference range indicator based on the results in SI units.
  - o Low: Result < reference range lower limit.
  - o Normal: Result  $\geq$  reference range lower limit AND result  $\leq$  reference range upper limit. o High: Result > reference range upper limit.

For clinical laboratory results below or above the limit of quantification will be handled as follows:

- Assign as equal to the limit of quantification, for example '<x' will be assigned as x for analysis purposes. SI conversions can be applied to the derived result. In the listings the result will be presented as the SI value (after conversion) with the qualifier symbol concatenated, for example '<y' in SI unit.

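### The by-group CMI overall-responder row and the maximum laboratory grade run past the Month 6 crossover, so neither is a ChAd3-EBO-Z versus Nimenrix comparison

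*SAP*

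**What the plan says.** References are to SAP v2 unless stated; v1 has the same CMI and laboratory rules.

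- **Columns.** SAP 6.3.1: "As a first step, safety and/or immunogenicity results will be presented by treatment administered at Day 0". A second step pools the data that follow ChAd3-EBO-Z in both groups.
- **Baseline.** SAP 6.2: "Baseline is defined as the last non-missing assessment (scheduled or unscheduled) prior to the first vaccination". Every later visit up to Month 12 is therefore post-baseline.
- **Crossover.** Under the vaccination schedule in the Protocol synopsis, the control group receives Nimenrix "at the Day 0 visit and the investigational ChAd3-EBO-Z vaccine at the Month 6 visit".
- **CMI overall response.** SAP 14.2.1: "The overall post-baseline response rate will also be included (response at any time point postbaseline"). The rule after Table 4 makes a single responding post-baseline visit sufficient: "If the subject is response at least one post-baseline visit, the subject will be regarded as an overall responder".
- **Pooled CMI table only.** "For the table pooled following the EBO-Z vaccination the overall response rate will only consider post-vaccination responses with 6 month of the EBO-Z vaccination". The SAP then lists Day 30 and Month 6 for the group vaccinated first, and Month 6 + 30 days and Month 12 for the control group.
- **Laboratory.** SAP 15.4.1: "Maximum grade overall will also be derived as the highest post-vaccination toxicity grade across all post-baseline visits and time points".
- **Size of the CMI sub-cohort.** SAP 5.5.1: "The first approximately 30 subjects randomised per age stratum and group, (180 subjects in total, 90 per group").

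**The concern.** Grouping by Day 0 treatment fixes the columns of a table. It does not say when follow-up stops. An any-visit summary in those columns, with no stop at Month 6, credits the control group with whatever follows its own ChAd3-EBO-Z dose.

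Protocol 11.8 and 11.9 recognise this overlap. They rule out setting the pooled post-ChAd3-EBO-Z data against control, because the controls later receive the vaccine. The two any-visit summaries bring the same overlap into the by-group tables.

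At stake is how a descriptive trial is read. Responder rate is a named tertiary endpoint. Laboratory abnormalities are a primary endpoint, although that endpoint is defined at named visits. A reader who takes the overall row as vaccine against control would see a smaller difference than the data contain.

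**Working it through.** **The plan's own figures.** The only design calculations are Protocol Tables 22 and 23. Clopper-Pearson limits with n = 300 reproduce all seven rows of Table 22 to four decimals (for example 0/300: 0 to 0.0122). The binomial tails for Table 23 are 0.897 to 0.910, against about 90% stated. The point challenges neither table. Their relevance is that Protocol 11.4 frames Table 22 for the period before the Month 6 vaccination.

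**Which rules carry a window.**

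| Summary | Limit written in the SAP? |
|---|---|
| Pooled CMI overall response (after Table 4) | Yes, 6 months after ChAd3-EBO-Z |
| By-group unsolicited and solicited AE incidence (15.1.2, 15.2.2) | Yes, events after the Month 6 dose are left out; added in v2 |
| Maximum platelet decrease (15.4) | Yes, Day 3 to Day 6 |
| By-group CMI overall response (14.2.1, 14.2.1.1) | No |
| Maximum laboratory grade (15.4.1) | No |

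The authors wrote a limit where they wanted one. A programmer following the text would include the later visits in the last two rows.

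**Visit count, control group.**
- CMI post-baseline visits are Day 30, Month 6, Month 6 + 30 days and Month 12. The last two follow ChAd3-EBO-Z: 2 of 4.
- Laboratory post-baseline visits are Day 3, Day 6, Day 30, Month 6, Month 6 + 6 days, Month 6 + 30 days and Month 12. The last three follow it: 3 of 7.

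The Month 6 sample is taken as pre-vaccination. This agrees with the pooled CMI rule, which counts Month 6 as a post-vaccination visit only for the group vaccinated first.

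**Size for CMI.** The documents give no response rates, so these inputs are assumptions: 5% background per visit, a 40% to 60% response 30 days after ChAd3-EBO-Z, and 80% of that (32% to 48%) at 6 months.

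Control group, visits independent:
- Day 30 and Month 6 only: 1 − 0.95² = 9.8%, about 9 of 90.
- All four visits: 1 − 0.95² × 0.60 × 0.68 = 63%, up to 1 − 0.95² × 0.40 × 0.52 = 81%, about 57 to 73 of 90.

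Without independence, an any-visit rate cannot fall below the largest single-visit rate, so the as-written control rate is at least 40% to 60%. The pre-crossover rate cannot exceed 5% + 5% = 10%. The rise is therefore at least 30 to 50 points under any dependence.

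Group vaccinated first, visits independent:
- Day 30 and Month 6 only: 1 − 0.60 × 0.68 = 59%, up to 1 − 0.40 × 0.52 = 79%. The gap to control is 49 to 69 points.
- All four visits, response back to background after Month 6: the control formula applies, 63% to 81%, and the gap is about 0.
- All four visits, 6-month response persisting: 1 − 0.60 × 0.68³ = 81%, up to 1 − 0.40 × 0.52³ = 94%. The gap is 18 points at the 40% response and 13 points at the 60% response.

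**Wider range.** Let f be the background per visit (1% to 10%) and R the probability of any response in the 6 months after ChAd3-EBO-Z (30% to 80%). The control rate moves from 1 − (1 − f)², that is 2.0% to 19.0%, to 1 − (1 − f)²(1 − R), that is 31.4% to 83.8%. An 11 to 78 point difference falls to about 0 if R is the same at both doses and the response does not persist past Month 6.

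**Laboratory illustration.** Assume a background g of 1% to 3% per visit and a vaccine-added probability e of 2.6% to 10%. Over Day 3 to Month 6 the difference is (1 − g)⁴ × e, that is 2.3 to 9.6 points. Over all seven visits both groups have 1 − (1 − g)⁷(1 − e), and the difference is about 0. That is the most masking possible, because it assumes that the later visits detect as much as the early ones. The schedule has no 3-day sample after the Month 6 dose.

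**The case against.** The strongest reply is that little else is touched. The same CMI table gives response at each time point with confidence intervals, so its Day 30 and Month 6 rows are clean comparisons, and the overall rate is an addition to them. The pooled overall rate is correctly windowed. Columns carry the sequence name (SAP Appendix 1), so the label shows that the controls later received ChAd3-EBO-Z. CMI is tertiary, every analysis is descriptive, and no test or decision rule uses the row. All of this stands, and it limits the harm to the any-visit summaries.

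Three stronger readings are tempting.

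- *A real T-cell effect would be hidden.* The by-visit and pooled results would still show it.
- *ChAd3-EBO-Z laboratory toxicity would be counted under Nimenrix, so that the vaccine looks no worse on a primary endpoint.* That endpoint is defined at named visits, and Protocol 11.8 asks for grades at each sampling point. The text does not show which table prints the maximum grade, and the table shells are not part of the documents. The shift table is not said to use it. For platelets, Protocol 9.1.5.1 reports that Phase 1 decreases occurred mostly on Day 1 and generally returned to baseline by Day 7. The first sample after the Month 6 dose is due 6 to 8 days later, so carry-over into the control maximum may be small.
- *The between-group contrast in the overall row disappears.* That requires the response in the group vaccinated first to fall to background after Month 6. If it persists, 13 to 18 points remain under the same model.

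The reply does not remove the core. As written, the overall row has no Month 6 limit, and a sequence label does not turn it into a vaccine-against-control comparison.

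**Conclusion.** The point holds for two summaries and no further. The by-group CMI overall-responder row and the maximum laboratory grade mix pre- and post-crossover visits in the control group. They are not a comparison of ChAd3-EBO-Z with Nimenrix, and they understate any vaccine effect in those rows. The row for the group vaccinated first likewise runs past its Nimenrix dose.

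The direction follows from the visit schedule; the size rests on the assumed rates. With 5% background and a 40% to 60% response, the control overall rate goes from about 10% to at least 40% to 60% (63% to 81% if visits are independent). The remaining gap depends on persistence.

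The case is strongest for the tertiary CMI responder rate and less certain for the laboratory maximum. It bears mainly on the final analysis. The interim analysis is triggered by Day 30 data but takes in whatever later data are available, so it could be affected in part. This should be fixed, but the trial's main results do not depend on it.

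**What to change.** In the by-group tables, for both groups:

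1. Derive overall CMI response from Day 30 and the Month 6 pre-vaccination sample only.
2. Derive maximum toxicity grade from Day 3 through the Month 6 pre-vaccination sample only.

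Report maxima after Month 6 separately by the vaccine received at Month 6, or leave the controls' post-ChAd3-EBO-Z data to the pooled tables already planned. SAP 15.4.1 should also name the table that prints the maximum grade.

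The cost is two SAP sentences and a visit filter in two programs, with a rerun of the affected outputs if they exist. No new data are needed.
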